12.5.2.3 Other Analysis of the Secondary Efficacy Endpoints

The secondary endpoints (not including PGIC endpoints) will be also analyzed for mITT and PP using the same analysis method described in Section 12.5.1. PGIC endpoint will be summarized by treatment group.

In addition, there will be a sensitivity analysis accounting for the individual pain scores influenced by the protocol-prohibited concomitant medications. In this analysis, the pain scores after receiving protocol-prohibited concomitant medication will be replaced with the baseline value only if a prohibited medication was used during the 10 days prior to Day 90 visit, Day 180 visit, Day 270 visit or the Day 365 visit.

12.5.3 Subgroup Analysis of Primary and Secondary Efficacy Endpoints

The subgroup analysis for the primary and secondary endpoints will be performed for the following factors:

- Baseline pain score of main study
- Baseline HbA1c of main study (< and ≥ median of main study)
- Gender (male and female)
- Age at informed consent (Study VMDN-003-2) (<65 years and ≥ 65 years)

For each subgroup of the ITT population, the primary and secondary endpoints will be summarized by treatment group and visit using descriptive statistics (n, mean, median, standard deviation, minimum, and maximum for the continuous variable and frequency and percentage for the categorical variable). Both types of descriptive summaries are also provided for the subgroups of study center and protocol version.

Participants will be assigned to a protocol version based on their randomization date and the date of Institutional Review Board (IRB) approval at their site.

The main analysis method described above for the primary and secondary endpoints will be used to analyze the treatment effect within each subgroup. Additionally, the possible treatment-by-subgroup interaction will be tested for each subgroup variable as follows:

- The interaction term for the subgroup variable and treatment group will be included in the analysis model. If the p-value of the interaction term is ≥ 0.05 , the treatment-by-subgroup interaction will be considered not statistically significant.

[REDACTED]

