8.1 Sample Size Considerations

The number of Participants to be enrolled in this 6-month extension study depends upon the number of subjects who complete the Day 180 Visit in Study VMDN-003-2 and provide written informed consent for this extension protocol (prior to or during their Day 180 Visit in the VMDN-003-2 study).

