10.6.1 Missing Pain Scores for the Average Scores from BPI-DPN

The means of the Average Daily Pain Scores (Question 5 from the BPI-DPN) for a visit will be considered as missing if fewer than 5 of 7 days of BPI-DPN eDiary entries are provided. Any missing mean pain score of ADPS will be imputed using the methods described below.

Multiple Imputation (MI) method:

- Step 1: Intermittent missing values will first be imputed by treatment group using the Markov Chain Monte Carlo (MCMC) method, resulting in data with a monotone pattern.
- Step 2: Multiple imputation by treatment group using linear mixed model regression with factors of baseline pain score, baseline HbA1c, gender, and age at informed consent (Study VMDN-003-2) will be applied to the data obtained from the MCMC step. The imputed score will be rounded to the first decimal point.

The entire procedure will be repeated 10 times, and 10 complete datasets will be used for the analysis.

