12.0 Statistical Methods

The primary analysis for this study will be performed and summarized after all randomized participants have had an opportunity to complete their 12-month follow-up visit.

The Safety Analysis will be based on the Safety population. The primary analyses of the efficacy endpoints will be based on the ITT population. Additional sensitivity analyses for the primary and secondary efficacy endpoints will be performed to further assess the effects of the treatment (Section 8.4.2 and 8.4.4).

The statistical analyses will be reported using summary tables, figures and listings. Continuous variables will be summarized with mean, standard deviation, median, minimum, maximum, 25th percentile, 75th percentile, and number of non-missing observations for each treatment group.

Categorical variables will be summarized by counts and by the percentage of participants in corresponding categories.

All inferential statistical analyses will be performed with a two-sided confidence level of 95% or a two-sided significance level of 0.05 unless otherwise noted.

All analyses and tabulations will be performed using SAS Version 9.4 or higher on a Server platform.

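### The treatment-by-subgroup interaction tests cut HbA1c and age in two, which gives up information that a continuous test would keep; baseline pain has no stated form

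*SAP*

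**What the plan says.** SAP 12.5.3 lists four subgroup factors for the primary and secondary endpoints. Two are continuous measurements cut in two: "Baseline HbA1c of main study (< and ≥ median of main study" (closing bracket omitted) and "Age at informed consent (Study VMDN-003-2) (<65 years and ≥ 65 years" (likewise). Gender is binary by nature. The fourth reads only "Baseline pain score of main study", with no cut and no statement of whether it enters as categories or as a number.

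Each subgroup gets descriptive summaries and a model-based treatment effect. A treatment-by-subgroup interaction is then tested for each variable: "The interaction term for the subgroup variable and treatment group will be included in the analysis model". The decision rule begins "If the p-value of the interaction term is ≥ 0.05", in which case the interaction is labelled not statistically significant. SAP 12.0 sets a "two-sided significance level of 0.05 unless otherwise noted".

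The SAP does not state outright that the cut version enters the interaction term. That is the natural reading, because the subgroup variables are defined by their cuts. The readable text plans no test with HbA1c or age kept continuous. In SAP 10.6.1 the imputation model names "factors of baseline pain score, baseline HbA1c, gender, and age at informed consent" without any cut, and SAP 12.5.1 declares baseline ADPS a continuous covariate.

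**The concern.** Cutting a continuous modifier treats everyone on the same side as alike. A participant just above the HbA1c median counts the same as one far above it. If the treatment effect changes gradually with HbA1c or age, the cut discards the gradient within each half, and the test misses a real trend more often than it needs to.

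What is at stake is the answer to who benefits, not whether the primary comparison succeeds. A non-significant p-value from a cut variable is weak evidence against modification, and it gives no estimate of how the effect changes per unit of the modifier. For baseline pain the gap is more basic: with no cut or form stated, two programmers could fit different tests.

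**Working it through.** **Plan's own figure.** There is none to reproduce. The documents state no power, effect size or sample size for the interaction tests. On enrolment, SAP 8.1 says: "The number of Participants to be enrolled in this 6-month extension study depends upon the number of subjects who complete the Day 180 Visit", subject to consent.

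**Inputs from the SAP.** HbA1c cut at the main-study median, age cut at 65 and interaction threshold 0.05 (12.5.3); two-sided testing at 0.05 (12.0).

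**Assumptions, because the documents are silent.** A normal modifier; a treatment effect that changes linearly with it; a share of participants above the cut of 50%, 30% or 20%; and a range of power for the continuous test. Residual SD, sample size and allocation ratio cancel in the relative comparison.

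**Step 1: information kept by a cut.** Relative efficiency (RE) is the squared correlation between the modifier and its cut version. For a normal modifier with share p above the cut, RE = φ(z_p)² / [p(1−p)], which is 2/π at the median.

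| Modifier and split | RE | Information lost | Sample-size equivalent (1/RE) |
|---|---|---|---|
| Normal, 50/50 | 0.637 | 36.3% | 1.57 |
| Normal, 40/60 | 0.622 | 37.8% | 1.61 |
| Normal, 30/70 | 0.576 | 42.4% | 1.74 |
| Normal, 20/80 | 0.490 | 51.0% | 2.04 |
| Uniform, 50/50 | 0.750 | 25.0% | 1.33 |

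For a right-skewed (log-normal) modifier with log-SD 0.1 to 0.5, a median cut loses 37% to 48%.

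**Step 2: power after the cut.** Power = Φ[(1.960 + z_power)·√RE − 1.960], plus a small opposite tail. Example at 80%, median cut: (1.960 + 0.842) × √0.637 − 1.960 = 0.275, and Φ(0.275) is about 61%.

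| Power if continuous | Median cut (points lost) | 30/70 cut (points lost) |
|---|---|---|
| 10% | 8.4% (1.6) | 8.1% (1.9) |
| 20% | 14.5% (5.5) | 13.6% (6.4) |
| 30% | 20.9% (9.1) | 19.3% (10.7) |
| 50% | 34.6% (15.4) | 31.8% (18.2) |
| 80% | 60.9% (19.1) | 56.6% (23.4) |
| 90% | 73.4% (16.6) | 69.1% (20.9) |
| 99% | 92.8% (6.2) | 90.2% (8.8) |

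**Step 3: simulation check.** A least-squares interaction test with an assumed 75 per arm, 4,000 runs and a slope set for 80% nominal power gave 78.1% continuous against 58.2% with the median cut, and 78.9% against 53.7% with the 30/70 cut. This agrees with Step 2 to within about three points. In null runs both codings rejected close to 5% of the time (4.4-5.9% continuous, 5.3% cut), so the continuous test does not gain power through extra false positives.

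**Step 4: the opposite truth.** If the effect is a pure step at the median, the cut loses nothing, and the linear continuous test keeps only 2/π = 64% of the information.

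**The case against.** The strongest reply is that the shape of any modification is unknown. Testing the same groups that are tabulated is coherent, and Step 4 shows that a linear test can be the weaker one. That stands as a real trade-off, and it is why the cut-point test should remain as supportive. The SAP, however, gives no reason to expect a step at the main-study HbA1c median or at age 65.

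It can also be said that the harm is limited. Model-based effects within each subgroup are already planned, so a gradient would not be hidden. That stands too. A reader might infer that the SAP would declare a uniform effect when p is 0.05 or more; it says only that the interaction is not statistically significant.

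Two other inferences go too far. One is that the HbA1c cut drifts with the analysed sample: the SAP ties it to the main study, so its value is fixed for this analysis, even if the extension participants do not divide exactly in half. The other is that baseline pain is also cut: no cut is given, and baseline pain already enters the primary model as a continuous covariate. Its defect is that its form in the subgroup analysis is unspecified.

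**Conclusion.** The point holds as a modest improvement. On the natural reading of SAP 12.5.3, the HbA1c and age interaction tests use cut variables. For a roughly normal modifier with a linear gradient, that costs about 36% of the information at a median cut and 42% at a 30/70 split.

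A reader might infer that this trial's tests will lose 36-42% of their information and some 20 points of power. The documents do not support that. The upper figure needs about 30% of participants on the smaller side of age 65, and no age distribution is given. A loss near 20 points needs a continuous test with roughly 60-90% power, and the extension has no sample-size target of its own. At 10-30% power the loss is about 2-11 points. Across the distributions examined the information loss ranges from 25% (uniform, median cut) to 51% (normal, 20/80), always assuming a linear gradient. The primary analysis is not touched.

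**What to change.** In SAP 12.5.3:

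- Make the main interaction test use baseline HbA1c, age and baseline ADPS as continuous moderators, one at a time, and keep gender as a class variable. This also settles the form for baseline pain.
- Add moderator, moderator-by-visit, treatment-by-moderator and treatment-by-visit-by-moderator terms, and take the Day 365 contrast. A lone treatment-by-moderator term in the four-visit model of SAP 12.5.1 would give one slope common to all visits, not the Day 365 gradient.
- Report the change in the Day 365 treatment difference per 1% HbA1c, per 10 years and per ADPS point, with 95% confidence intervals combined over the imputed datasets. For the responder model of SAP 12.5.2.2, report the change in the log odds ratio.
- Keep the categories for descriptive tables and within-subgroup estimates, and the cut-point interaction p-value as supportive. If baseline pain is to be shown in categories, state its cut.

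The cost is SAP wording and a few model terms; no new data are needed. With two arms and four visits, each moderator adds 1 + 3 + 1 + 3 = 8 fixed effects to the continuous model, or 7 for baseline ADPS, whose main effect is already there. The downside is that a pure step at the cut is detected less well by the linear test, which is why the cut-point result is retained.

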12.6 Safety Analyses

Safety analyses in this study will evaluate the safety profile of Engensis as compared with control. No formal statistical testing will be conducted for the safety analyses. The following sections summarize the descriptive analysis methods for these safety endpoints. All participants in the Safety population will be included in these analyses. Participants will be grouped by treatment administered. All summaries will be derived based on available data in the extension study only. No imputation will be performed for missing values.

- Adverse events of special interest (AESI) by preferred term. An Excel spread sheet/listing will be generated for all TEAEs/TEAEs designated to be AESIs in the EDC database and sent to the Medical Monitors for review. The Medical Monitors will be blinded while reviewing the AESIs and will assign each AESI to one of the three main categories, including the subcategories for angiogenesis and AESIs related to other medical problems. When all AESIs have been assigned to a category by the Medical Monitors, the Excel spreadsheet/listing will be returned to the statistician. The statistician will break the blind and assign the participants with each of these AESIs to the appropriate treatment group and then, will generate appropriate tables and listings.

AESI summary tables will also be presented separately for each level of the randomization stratification factor.

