8.4.5. Adverse Events of Special Interest

Categories of AESIs

There are three main categories of AESIs: 1) those considered to be related to the angiogenesis potential of Engensis, 2) other medical problems in this patient population, and 3) COVID-19 infections occurring in Participants during the study.

8.4.5.1. **AESIs Related to Angiogenesis**

Atherosclerosis

Hyperplasia of the vasa vasorum in the early stages of atherosclerosis is independent of angiogenesis, but the intimal neovascularization that follows the hyperplasia of the vasa vasorum

Version 1.0 42 Final: 11 Feb 2021

is angiogenesis-dependent.³⁵ Angiogenesis increases oxygen and nutrients to the artery wall and supports initial plaque growth. Once the atherosclerotic plaque develops, intimal angiogenesis is thought to contribute to characteristics of an unstable plaque, plaque hemorrhage, and plaque rupture. Therefore, diagnoses suggestive of recent coronary artery disease or cerebral vascular disease from the Day 180 Visit (VMDN-003-2) to the Day 365/ET Visit (VMDN-003-2b) will be evaluated as AESIs.

Proliferative diabetic retinopathy

Neovascularization is an advanced stage of diabetic retinopathy that is due to relentless abnormal fibrovascular proliferation.³⁶ Because the angiogenic potential of Engensis may promote the development of or stimulate abnormal fibrovascular proliferation in the retina, new fundoscopic changes or symptoms of proliferative diabetic retinopathy that occur from the Day 180 Visit (VMDN-003-2) to Day 365/ET (VMDN-003-2b) are considered AESIs.

Cancer

Angiogenesis plays an important role in the proliferation and metastatic spread of cancer as these processes are dependent on an adequate supply of oxygen and nutrients and removal of waste products.³⁷ All types of cancer reported between the Day 180 Visit (VMDN-003-2) to Day 365/ET (VMDN-003-2b) will be deemed to be AESIs.

Diabetes mellitus and obesity (BMI ≥30) each increases the risk of several types of cancer. ^{38,39} In type 2 DM, there is a 2- to 3-fold increased risk for pancreatic cancer, a 2-fold increased risk for hepatobiliary and endometrial cancers, a 50% increased incidence of colorectal cancer, and a 20% increased risk for breast cancer. ⁴⁰ Obese postmenopausal women have an increased risk of breast cancer, ⁴¹ and obesity is associated with a modestly increased risk of colorectal cancer, ^{42,43} pancreatic cancer, ⁴⁴ and prostate cancer. ⁴⁵

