8.4.5.2. AESIs Related to Other Medical Problems

Several medical problems are frequently observed in patients with diabetic peripheral neuropathy that should be considered AESIs. These medical problems are listed below by type of medical problem.

Infections and Infestations; Skin and Subcutaneous Disorders

Because patients with diabetic peripheral neuropathy are at an increased risk to develop skin lesions (e.g., blisters, ulcers) and various lower limb infectious complications (e.g., cellulitis, osteomyelitis) that may be associated with systemic infections (e.g., bacteremia, sepsis, or septic shock), all of these types of medical problems that occur between the Day 180 (VMDN-003-02) and the Day 365/ET (VMDN-003-2b) Visits will be considered AESIs. In addition, any amputations involving the lower extremity, development of Charcot foot, or other similar complications will also be considered AESIs.

Peripheral Arterial Disease

An overlap of DPN and peripheral artery disease (PAD) apparently exists in type 2 diabetic patients. ⁴⁶ Because Participants with DPN may develop signs or symptoms of PAD between the Day 180 (VMDN-003-2) and the Day 365/ET (VMDN-003-2b) Visits, detailed evaluations of Participants considered to have PAD will be considered AESIs.

Version 1.0 43 Final: 11 Feb 2021

Diabetic Neuropathies

Because Participants in this study may develop other types of diabetic peripheral neuropathies while in the study, the following events will be considered to be AESIs in Participants with DPN: diabetic mononeuropathy, diabetic mononeuropathy multiplex, and diabetic polyradiculopathy. The occurrence of these other types of peripheral neuropathies in a Participant with DPN may indicate a more severe form of DPN.

Because Participants in this study may develop various manifestations of autonomic neuropathy (typically involves the gastrointestinal, genitourinary tract, cardiovascular systems) after randomization, the clinical manifestations of diabetic autonomic neuropathy will be considered to be AESIs.

Glycemic Control

Hypoglycemia, hyperglycemia, hyperlipidemia, hypercholesterolemia, and hypertriglyceridemia are to be listed as AESIs based on the Common Terminology Criteria for Adverse Events (CTCAE) grading if they are Grades 3 or 4.

Metabolic complications of DM (such as diabetic ketoacidosis [DKA], hyperglycemic hyperosmolar non-ketotic coma, lactic acidosis, metabolic acidosis [overlaps with DKA]) are to be listed as AESIs.

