10.1.7. Data Management

All Participant data will be entered into a password-protected validated EDC system by authorized Site personnel according to the CRO's SOPs.

Data discrepancies identified via programmed edit checks, manual data review or discovered during data monitoring will be addressed and resolved. An audit trail in the EDC system will list all changes made to the data, with a date/time stamp and user initials. Upon database lock, occurring after data are declared clean and eCRFs have been approved by the Investigator, the CRO will provide SAS datasets to the Sponsor and designated Statistician for data analysis via secure data transfer specified in the Study Data Management Plan.

Version 1.0 57 Final: 11 Feb 2021

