10.2.4. Recording and Follow-Up of TEAEs and/or TESAEs

AE and TESAE Recording

- When an AE/TESAE occurs, it is the responsibility of the Investigator to review all
 documentation (e.g., hospital progress notes, laboratory reports, and diagnostics
 reports) related to the event.
- The Investigator will then record all relevant TEAE/TESAE information in the CRF.
- It is not acceptable for the Investigator to send photocopies of the Participant's medical records to the Sponsor or designee in lieu of completion of the TEAE/TESAE CRF page.
- Instances may arise when copies of medical records for certain cases are requested by the Sponsor or designee. In this case, all Participant identifiers, with the exception of the Participant number, will be redacted on the copies of the medical records before submission to the Sponsor or designee.

Version 1.0 63 Final: 11 Feb 2021

 The Investigator will attempt to establish a diagnosis of the event based on signs, symptoms, and/or other clinical information. Whenever possible, the diagnosis (not the individual signs/symptoms) will be documented as the TEAE/TESAE.

Assessment of Intensity

The Investigator will make an assessment of intensity for each TEAE and TESAE reported during the study and assign it to 1 of the following categories:

- Mild: An event that is easily tolerated by the Participant, causing minimal discomfort and not interfering with everyday activities.
- Moderate: An event that causes sufficient discomfort and interferes with normal everyday activities.
- Severe: An event that prevents normal everyday activities. An TEAE that is assessed as severe should not be confused with an TESAE. Severe is a category used for rating the intensity of an event; and both AEs and SAEs can be assessed as severe.

An event is defined as "serious" when it meets at least 1 of the predefined outcomes as described in the definition of an TESAE, NOT when it is rated as severe.

Assessment of Causality

- The Investigator is obligated to assess the relationship between study intervention and each occurrence of each TEAE/TESAE.
- A "reasonable possibility" of a relationship conveys that there are facts, evidence, and/or arguments to suggest a causal relationship, rather than that a relationship cannot be ruled out.
- The Investigator will use clinical judgment to determine the relationship.

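### The SAP fills the AESI tables only from events designated as AESIs in EDC, with no check against the protocol's rule-based AESI definitions

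*SAP*

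**What the plan says.** **SAP 12.6.1 (AESI bullet).** The review starts from one listing: "An Excel spread sheet/listing will be generated for all TEAEs/TEAEs designated to be AESIs in the EDC database and sent to the Medical Monitors". The monitors, blinded at this point, "will assign each AESI to one of the three main categories", with subcategories for angiogenesis and for other medical problems. The statistician then breaks the blind and tabulates. The AESI tables are repeated for each level of the randomization stratification factor.

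**Protocol 8.4.5.** AESI status is set by definition. For cancer: "All types of cancer reported between the Day 180 Visit (VMDN-003-2) to Day 365/ET (VMDN-003-2b) will be deemed to be AESIs". New proliferative retinopathy, recent coronary or cerebrovascular diagnoses, lower-limb skin lesions and infections, and metabolic complications such as ketoacidosis also qualify by rule. Hypoglycemia, hyperglycemia, hyperlipidemia, hypercholesterolemia and hypertriglyceridemia qualify "based on the Common Terminology Criteria for Adverse Events (CTCAE) grading if they are Grades 3 or 4".

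**Protocol 8.4.3 and Appendix 2.** Section 8.4.3 refers to Appendix 2 for how AESIs are recorded. Appendix 2 (10.2.4) gives a three-level intensity scale based on everyday functioning. Its top level reads "Severe: An event that prevents normal everyday activities". Appendix 2 contains no rule for designating an AESI and no CTCAE grading.

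**Protocol 10.1.7.** On data entry: "All Participant data will be entered into a password-protected validated EDC system by authorized Site personnel".

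**The concern.** The protocol says which events are AESIs. The SAP counts the events that carry a designation. The two agree only if every qualifying event has been designated, and nothing in the plan tests that. The monitors are the natural people to test it, but the task described for them is to categorise events already on the list.

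The AESI output is the only listed adverse event summary that groups events by angiogenesis subcategory. Protocol 2.3.1 shows why that grouping is of interest: the five serious events so far reported as possibly related include colon cancer, adenocarcinoma, myocardial infarction and vitreous hemorrhage. Such events are likely to be few, so a reader of the AESI table needs to know whether it counts all events that meet the definition or only those that were designated.

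**Working it through.** The documents state no AESI count, rate or designation sensitivity, so there is no figure to reproduce. The check sets the sections side by side.

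**1. Routes into the AESI tables.** SAP 12.6.1 gives one, the EDC designation. Neither document describes a search of undesignated TEAEs by MedDRA term, an application of the 8.4.5 definitions to coded data, or a comparison of laboratory values with AESI records.

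**2. Cancers, vascular events, infections, metabolic complications.** No grade is needed for these; the protocol rule decides. The only way such an event, once recorded as a TEAE, can be missing from the AESI tables is that it was not designated.

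**3. The five glycemic and lipid terms.** These "are to be listed as AESIs based on the Common Terminology Criteria for Adverse Events (CTCAE) grading if they are Grades 3 or 4". Three pieces are needed to apply that rule:
- *A CTCAE version.* None is named. CTCAE appears only in protocol 8.4.5.2 and nowhere in the SAP.
- *A recorded or derived grade.* The only scale described is the functional one in 10.2.4.
- *A link from laboratory values to AESI status.* None is described.

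**4. What still shows an undesignated event.**

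| Display | What it covers | What it does not do |
|---|---|---|
| TEAE and serious TEAE tables (SAP 12.6.1) | Every recorded TEAE by SOC and preferred term, by arm | Group by AESI category |
| Laboratory counts (SAP 12.6.3) | Glucose above 320 mg/dL, triglycerides at or above 500 mg/dL, LDL at or above 189 mg/dL | Set a low-glucose or total-cholesterol limit; link to CTCAE or AESI status |
| Fundoscopy (SAP 12.6.4) | Proliferative retinopathy by arm, whatever the designation | Use the AESI window: it compares with main-study screening, while the AESI window opens at Day 180 |
| Blinded data screening (SAP 10.0) | Questionable values go to the CDRC | Reconcile AESIs |

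The loss is therefore confined to the AESI tables, overall and by stratum. It is not a loss from the safety report.

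**5. How much an imbalance could be distorted (illustration only).** Assume 11 true AESIs split 8 v 3, with each designated independently with probability s. These inputs are invented to show scale.
- Expected counts are 8s v 3s: 6.4 v 2.4 at s = 0.80, and 4.8 v 1.8 at s = 0.60. The ratio stays at 8/3 = 2.67.
- P(at least one missed) = 1 − s^11: 0.43 at s = 0.95, 0.91 at s = 0.80, 0.996 at s = 0.60.
- P(the excess disappears) = P(X ≤ Y), with X ~ Bin(8, s) and Y ~ Bin(3, s): about 0.001% at s = 0.95, 0.6% at s = 0.80, 6% at s = 0.60.

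Some under-counting is likely under these assumptions, but complete masking of such an imbalance is not.

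**The case against.** The strongest case against the point is that little is really hidden. Every recorded TEAE is tabulated by arm, and protocol 10.2.3 names invasive or malignant cancers as examples of events usually considered serious, so these should also reach the serious TEAE table. Retinal findings and high laboratory values have their own displays, and safety is descriptive with no formal testing. This stands, and it limits the harm to the AESI tables.

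Several stronger readings are tempting, and the documents do not support them:
- *Sites under-flag.* The SAP does not say who designates. Protocol 10.1.7 makes sites a reasonable inference, no more.
- *The monitors never see other TEAEs.* The SAP describes one listing; it does not limit what else they see.
- *The record holds no CTCAE grade.* The functional scale and a CTCAE grade could coexist. CRF version 3.0, on which the SAP rests, is not available, and a CTCAE field, AESI prompt or edit check cannot be excluded.
- *Missed events would hide or create an imbalance.* The illustration above shows that the excess seldom vanishes, even on invented inputs.
- *Laboratory values should be graded into AESIs by program.* Protocol 10.2.1 excludes from AEs those abnormalities associated with the underlying disease unless they are more severe than expected. Section 8.4.9 can be read more broadly, which leaves the treatment of a high glucose unsettled. Glucose is also a random sample (8.3.5.1.4). Automatic grading could label as AESIs values that are not AEs.

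What remains after all this is the missing reconciliation, which none of the existing displays supplies.

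**Conclusion.** The point holds in a limited form. The SAP counts designated AESIs, the protocol defines AESIs by rule, and the plan has no step that brings the two together. A qualifying event that is not designated is left out of the AESI tables but remains in the general TEAE tables if it was recorded as an AE. The CTCAE gap applies only to the five glycemic and lipid terms; for the other categories the sole risk is a missed designation.

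The size of any under-count cannot be estimated from the documents, and could be nil if the CRF prompts for AESIs and sites respond fully. The conclusion rests on the SAP text as written and assumes that no CRF guideline or data management document supplies the missing check. If one does, the SAP should cite it. This is a worthwhile, inexpensive improvement to the AESI analysis; it does not show that safety events go unreported.

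**What to change.** Amend SAP 12.6.1, to be carried out before unblinding:

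1. Fix in advance a MedDRA preferred-term list for each 8.4.5 category and run it over all coded TEAEs. Alternatively, list all TEAEs.
2. Send the blinded hits to the Medical Monitors together with the EDC-designated events.
3. Count an event as an AESI if it meets 8.4.5. Show designated and reviewer-added events separately, overall and by stratum.
4. For the five glycemic and lipid terms, name the CTCAE version and say how the grade is recorded or derived. Where a central laboratory value suggests a qualifying event and there is no AESI record, raise a blinded query to the site or Medical Monitor. Do not convert the value into an AESI automatically.
5. State who makes the EDC designation.

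The cost is SAP wording, one search list, one longer listing for reviewers already named, and a few hours of blinded review. AESI counts may rise slightly; the separate display of added events makes any rise visible. No clinical rule changes.
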